## 5 STUDY OBJECTIVES

**This is an exploratory study to:**

- assess cognitive outcomes in stable renal transplant patients treated with twice-daily oral tacrolimus at baseline and following conversion to ENVARSUS XR, and

- assess quality of life in patients after renal transplantation treated with twice-daily oral tacrolimus at baseline and following conversion to ENVARSUS XR.

[figure not shown]
## 6 STUDY DESIGN

### 6.1 Overall Study Design

This is an open-label, single site, prospective Phase 4 clinical study to assess tacrolimus-induced cognitive impairment in stable kidney transplant patients converted from oral twice-daily TAC-IR to ENVARSUS XR once daily. Approximately 60 adult male or female patients who received a primary or secondary kidney transplant 4 weeks to 10 years prior to study start will be enrolled.

The study design is depicted in [Figure 6-1](#). Patients will be required to have been receiving a stable regimen of TAC-IR (i.e., no dose adjustments) for a minimum of 4-7 days prior to Baseline. At Baseline, patients will be switched to ENVARSUS XR for a total of 3 months.

**Figure 6-1 Study Design Diagram**

At screening visit (Visit 1), a minimum of 4-7 days on stable dose of TAC-IR formulation will be confirmed, informed consent will be documented, and eligibility review, including the Beck Depression Inventory (BDI-II), will be performed.

On Visit 2, a sequence of cognitive tests will be administered after the morning dose of TAC-IR in the following order: Repeatable Battery for the Assessment of Neuropsychological Status Update (RBANS Update); Trail Making Test A & B (TMT-A, TMT-B); and in addition, a Demographics Survey, the WHODAS, a quality of life measure, and the Pittsburgh Insomnia Rating Scale (PIRS-20) will also be completed by patients prior to the cognitive tests. Patients will take their last dose of TAC-IR in the evening of Visit 2 or combined Visit 1/Visit 2, and ENVARSUS XR will be prescribed and started as soon as possible but no later than the next 30 days

On Visit 3, after their morning dose of ENVARSUS XR, the same sequence of cognitive tests will be administered in the order noted above, PGI-I will be assessed prior to the administration

of WHODAS and PIRS-20. Additionally, the CGI-I will be completed by the Investigator after all the assessments are completed for the visit.

At Visit 4 after their morning dose of ENVARSUS XR, same activities as Visit 3 are repeated.

Please refer to [Section 10](#) for additional information on study visits and activities.

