## Study Design Diagram:

■ Renal transplantation at least 4 weeks but no more than 10 years prior to date of screening

★ Study assessments, per schedule of assessments

△ Switch all subjects to ENVARSUS XR: Envarsus should be started as soon as possible but no later than 30 days after Visit 2 or combined Visit 1/Visit 2

\* Subjects who discontinue ENVARSUS XR prior to Visit 4 will complete an early withdrawal visit

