d Whole blood for tacrolimus trough level (prior to the morning dose of tacrolimus) can be drawn on Day -1 such that the results are available for the determination of patient eligibility at Visit 2, in which case the draw does not need to be repeated at Visit 2.

e Pregnancy test must be completed for women of childbearing potential prior to enrollment.

f AE/SAE collection begins after the first dose of ENVARSUS XR.

g At enrollment patients should be prescribed a minimum of 4 months' supply; patients should be prescribed ENVARSUS XR at the end of Visit 3 (4-month supply), and/or SOC visit for ENVARSUS XR dose adjustment as needed.

h Patients will begin taking ENVARSUS XR as soon as possible but no later than the next 30 days.

i Labs should be charged to study if the visits don't coincide with standard of care of visits

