#### 8.3.2 Interruption of Therapy with a Study Drug (ENVARSUS XR)

Patients who require interruption of immunosuppressive therapy for clinical cause anytime between Visit 2 and 3 will be required to be on a stable dose of ENVARSUS XR for a minimum of 4 days before Visit 3 assessments are performed.

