## 9.2 Study Drug Dosing and Administration

ENVARSUS XR tablets will be administered orally q.d. in the morning based on a conversion factor from tacrolimus to ENVARSUS XR of 1:0.8 (see [Appendix 2 or https://www.envarsusxr.com/hcp/professional-resources/envarsus-xr-dose-converter/](https://www.envarsusxr.com/hcp/professional-resources/envarsus-xr-dose-converter/) and [PI discretion](#)) to maintain target trough level of 3-9 ng/mL. The following dosing instructions should be observed:

- Patients should take ENVARSUS XR on an empty stomach at the same time of the day, preferably in the morning (to ensure consistent and maximum possible drug exposure).
- Patients should swallow ENVARSUS XR whole with fluid (preferably water) and should not chew, divide, or crush the tablets.
- If a dose is missed, the patient should take it as soon as possible within 14 hours after the scheduled time and inform the study investigator; beyond the 14-hour time frame, the patient should wait until the usual scheduled time to take the next regular daily dose.
- Patients should avoid eating grapefruit or drinking grapefruit juice or alcoholic beverages while taking ENVARSUS XR.

Patients should be encouraged to take their study treatment on a consistent schedule with regard to time of day and relation to meals except on their study visit days. Patients will be instructed not to take their morning dose of TAC-IR prior to their clinic visit (Visit 2) but to take their morning concomitant medications as they normally would. Once at the clinic at Visit 2, after the TAC-IR trough level blood sample has been drawn, the patient will take the morning dose of TAC-IR. ENVARSUS XR will be prescribed, and patients will be instructed to begin taking ENVARSUS XR the following morning.

Likewise, for Visit 3, patients will be instructed not to take their morning dose of ENVARSUS XR prior to their clinic visit (Visit 3), after the ENVARSUS XR trough level blood sample has been drawn, the patient will take the morning dose of ENVARSUS XR.

For Visit 4, patients will be instructed not to take ENVARSUS XR before coming to the clinic; after their ENVARSUS XR trough blood draw and other procedures for the visit, they will take their last single daily dose of ENVARSUS XR.

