#### 10.1.2 Enrollment (Visit 2)

Note that the designation of Visit 2 as occurring on 'Day 0' is meant to reflect that ENVARSUS XR dosing is to start as soon as possible but no later than the next 30 days. Visit 1 and Visit 2 may be combined if no dose adjustments were performed and the patient has been maintained on a

stable dose of TACIR with trough level between 3-9 ng/mL, and the physician does not deem any dose adjustment required.

Upon arrival at the clinic at Visit 2 the following assessments will be performed:

- Prior to the morning dose of TAC-IR, the patient will have approximately 5 mL of whole blood drawn for the assessment of TAC-IR trough.
- After confirmation of patient eligibility, a blood drawn for safety laboratory parameters (approximately 15 mL, for complete blood count [CBC] and a metabolic profile [blood glucose, calcium, sodium, potassium, CO2 (carbon dioxide, bicarbonate), chloride, blood urea nitrogen (BUN) and creatinine]).
- Physical examination and vital signs measurements.
- Patients will then be instructed to take their morning dose of TAC-IR.
- QoL and cognitive tests will then be performed after the morning TAC-IR dose in the following order:
  - WHODAS; ○ PIRS-20; ○ RBANS, ○ TMT-A and TMT-B;
  - After cognitive tests, ENVARSUS XR will be prescribed and patients will be instructed to take the first dose of ENVARSUS XR as soon as possible but no later than the next 30 days . Patients must be instructed to take their evening dose of TAC-IR.
- Concomitant medication use (including compliance to immunosuppressive therapy and adequate drug supply) and the safety monitoring processes will be initiated.
- Prior to leaving the clinic, the patient will be prescribed ENVARSUS XR with instructions to take the medication as soon as possible but no later than the next 30 days prior to noon each day for the remainder of the study. Patients will be reminded not to take their daily dose of ENVARSUS XR prior to their clinic at Visit 3 and to bring all remaining ENVARSUS XR medications to that visit.

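### Section 6.1 ends TAC-IR on the evening of Visit 2 but lets ENVARSUS XR start up to 30 days later, and nothing tells a delayed starter to stay on TAC-IR

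*Combined protocol and SAP*

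**What the plan says.** Section 6.1, in the text under Figure 6-1, fixes the end of the old drug: "Patients will take their last dose of TAC-IR in the evening of Visit 2 or combined Visit 1/Visit 2". The same sentence then gives the start of the new one: "ENVARSUS XR will be prescribed and started as soon as possible but no later than the next 30 days".

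The 30-day window appears in several other places:
- Synopsis, Study Design Diagram: "Switch all subjects to ENVARSUS XR: Envarsus should be started as soon as possible but no later than 30 days after Visit 2".
- Synopsis, Study Visits, Visit 2. This is the only text that addresses a patient who cannot begin the next morning, and it says only that the Visit 3 date moves.
- Schedule of Study Activities, footnote h: "Patients will begin taking ENVARSUS XR as soon as possible but no later than the next 30 days".
- Section 10.1.2, which repeats the window and adds "Patients must be instructed to take their evening dose of TAC-IR".

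Section 9.2 describes a different plan, an immediate switch: "ENVARSUS XR will be prescribed, and patients will be instructed to begin taking ENVARSUS XR the following morning".

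**The concern.** The last-dose clause fits the next-morning start in Section 9.2: an evening TAC-IR dose, then ENVARSUS XR the next morning. It does not fit a start days or weeks later. For such a patient Section 6.1 ends one drug without starting the other, and no other section says what to take in between.

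What is at stake is patient safety. The appended label (section 2.1) warns that underexposure to tacrolimus can lead to graft rejection. Three features of the protocol sharpen this:
- Patients may be as little as 4 weeks after transplant.
- Mycophenolate and prednisone are permitted but not required, so tacrolimus could be the only immunosuppressant.
- Adverse event collection starts only after the first ENVARSUS XR dose, and the schedule has no study trough between Visits 2 and 3. A lapse before the switch could go unrecorded.

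Delayed starts are foreseen. The amendment summary says the window was added so that patients could get access to ENVARSUS XR.

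**Working it through.** **Does any section tell a delayed starter to continue TAC-IR?**

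| Place | What it gives a delayed starter |
|---|---|
| Section 6.1 | Last TAC-IR dose on the evening of Visit 2 |
| Synopsis, design diagram | Dates the switch at the ENVARSUS XR start; no TAC-IR instruction |
| Synopsis, Visit 2 | Move Visit 3; no TAC-IR instruction |
| Schedule, footnote h | Window only |
| Section 8.3.2 | Covers "Patients who require interruption of immunosuppressive therapy for clinical cause"; not a wait for drug |
| Section 9.1 | TAC-IR comes from the patient's own supply; no duration |
| Section 9.2 | Assumes a next-morning start |
| Section 10.1.2 | One evening dose; nothing for later days |
| Section 14.3.1 | Expects enrollment and first dose on the same date |

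None supplies the instruction.

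**Length of the literal gap.** The plan gives no figure to reproduce. Assume the last TAC-IR dose at about 20:00 on Day 0 and the first ENVARSUS XR dose at about 08:00 on Day k. These clock times are assumptions.

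Gap = 24k − 12 hours; uncovered twice-daily doses = 2(k − 1).

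- Day 1: 12 h, 0 doses.
- Day 7: 156 h, 12 doses.
- Day 30: 708 h (29.5 days), 58 doses.

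**How quickly levels fall.** Inputs:
- Entry troughs of 3-9 ng/mL (inclusion criterion 5).
- Half-lives of 31.0 h and 48.4 h (label section 12.3, Excretion).
- Lower bound of 3 ng/mL, from the study's target range.

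A trough is reached about 12 h after a twice-daily dose. With first-order decay:

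Hours after last dose = 12 + half-life × log2(starting trough / 3).

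| Starting trough (ng/mL) | Half-lives to reach 3 ng/mL | Hours after last dose | Days |
|---|---|---|---|
| 9 | log2(9/3) = 1.585 | 12 + 49.1 = 61.1, to 12 + 76.7 = 88.7 | 2.5 to 3.7 |
| 6 | log2(6/3) = 1 | 12 + 31.0 = 43.0, to 12 + 48.4 = 60.4 | 1.8 to 2.5 |
| 4 | log2(4/3) = 0.415 | 12 + 12.9 = 24.9, to 12 + 20.1 = 32.1 | 1.0 to 1.3 |
| 3 | 0 | 12 | 0.5 (no margin) |

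The label's conversion range starts at 4 ng/mL (section 2.3). Against that floor, a patient starting at 9 ng/mL has log2(9/4) = 1.170 half-lives, so 12 + 36.3 = 48.3 h to 12 + 56.6 = 68.6 h, or 2.0 to 2.9 days.

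**After the correction.** If TAC-IR continues to the evening before the first ENVARSUS XR dose, the gap is about 12 h with no uncovered doses, whatever the start day.

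**The case against.** The strongest reply is that nobody chose a tacrolimus-free interval, and that the documents point the other way:
- The synopsis says troughs are monitored to keep exposure in the therapeutic range.
- The patient holds a personal TAC-IR supply (Section 9.1), so waiting for ENVARSUS XR does not interrupt it.
- Section 6.1 refers the reader to Section 10. There, Section 10.1.2 speaks of an evening dose without calling it the last, and checks concomitant medication "including compliance to immunosuppressive therapy and adequate drug supply".
- Sections 9.2 and 14.3.1 treat an immediate switch as the norm.

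Harm would need a delayed starter and also staff who let a kidney recipient stop tacrolimus on the strength of one clause.

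This stands as evidence of intent. A reader might infer that the protocol plans a washout of up to 30 days; the documents do not support that. Nor do they support the inference that the pre/post cognitive comparison is compromised: if TAC-IR continues, it is not materially affected.

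The reply does not remove the defect. None of these places gives the instruction, and relying on clinicians to disregard a written dosing rule is not a safeguard.

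The decay figures also have limits. The half-lives come from healthy subjects, one of them on ENVARSUS XR, and their reported SDs (8.1 and 12.3 h) are not carried through. A reader might take the upper rows of the table to mean that a delay of two or three days is harmless. That does not follow, because a patient entering at 3 or 4 ng/mL has little or no margin.

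**Conclusion.** The concern holds as an internal contradiction in a stated dosing rule, wrong as written for delayed starters only. It is not a design choice, and continued TAC-IR is almost certainly what was meant. Because the literal text leaves a transplant recipient without tacrolimus, it needs correcting despite the clear intent.

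Under the literal text, levels would fall below 3 ng/mL about 1 to 4 days after the last dose for starting troughs of 4 to 9 ng/mL, and sooner at the bottom of the entry range. This rests on first-order decay, a trough 12 h after dosing, and healthy-subject half-lives applied to kidney recipients, so it is illustrative. The 29.5-day gap is the literal worst case, not an expected outcome. The number of late starters is not given, so no expected number of affected patients can be stated.

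**What to change.** Delete the last-dose clause from Section 6.1. In its place, and in Sections 9.2 and 10.1.2, footnote h and the synopsis Visit 2 text, state:

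*Patients continue TAC-IR, with any medically necessary dose adjustment, until the evening before their first ENVARSUS XR dose. ENVARSUS XR starts the next morning where possible, and within 30 days of Visit 2 at the latest.*

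The synopsis Visit 2 text must be included because it is the only place that deals with patients who cannot start the next morning. The phrase on dose adjustment matters because a requirement to stay on a stable dose could be read as barring a needed TAC-IR change during the wait.

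The cost is one replacement text in five places. No visit, laboratory test or procedure is added. A separate TAC-IR stop-date field is unnecessary, since the corrected rule ties that date to the ENVARSUS XR start.

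Table 10-1 counts Visits 3 and 4 from Visit 2, while the synopsis counts from the ENVARSUS XR start. That is a separate, minor alignment point and is not needed for this correction.

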## **6.2 Study Endpoints**

### **6.2.1 Primary Efficacy Endpoint**

The primary efficacy endpoint is the change in cognitive function from Visit 2 to 3 as measured by the Global Cognition Score on the RBANS, a composite score reflecting performance in areas of immediate and delayed memory, visuospatial construction, language, and attention.

### **6.2.2 Secondary Efficacy Endpoints**

The secondary efficacy endpoints include the following:

- Change in cognitive function from Visit 2 to 3 as measured by the following:
- TMT-A and TMT-B (visual scanning speed/visual attention)
- Change in QoL from Visit 2 to 3 and from Visit 2 to 4 as measured by the WHODAS
- PGI-I and CGI-I at Visit 3
- Change in quality of sleep from Visit 2 to 3 as measured by the PIRS-20

### **6.2.3 Safety Endpoints**

The safety endpoints in this study are the incidence of AEs, SAEs, and discontinuations due to AEs.

## **7 RATIONALE FOR STUDY DESIGN**

The open-label switch study design provides the benefit of having patients serve as their own control, thus minimizing other confounding factors that may impact cognitive function and/or other measurements.

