| Methodology:

An open-label, single center, prospective Phase 4 clinical study to assess tacrolimus-induced cognitive outcomes in stable kidney transplant patients converted from oral tacrolimus twice daily immediate-release (TAC-IR) to ENVARSUS XR (tacrolimus extended-release tablets; Veloxis Pharmaceuticals, Inc.) once daily (q.d.). The study is designed to determine if the test drug, ENVARSUS XR, is associated with improved cognitive function relative to that observed with tacrolimus treatment. Each therapy may be concomitantly administered with mycophenolate mofetil (MMF) and/or mycophenolate sodium (MPS), including generic versions of each, as long as doses remain stable during the screening period through Visit 3 of the study. All prophylaxis and other medication will be allowed per standard of care (SOC). Medications that inhibit or induce cytochrome P450 3A (CYP3A) are allowed only if medically necessary, but when using such agents, increased monitoring of tacrolimus drug concentrations is recommended. Stable renal transplant patients are defined as patients who are recipients of a renal transplant 4 weeks to 10 years prior to screening and have received a stable dose (i.e., no dose adjustments) of TAC-IR for a minimum of 4-7 days at the time of screening. Following baseline, study visits will be conducted over a 8-month treatment period with ENVARSUS XR.
 |                                |

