## **Study Population:**

### Inclusion Criteria

1. Patients must be able to understand English and provide written informed consent;
2. Males and females between 18 and 80 years of age;
3. Recipients of a primary or secondary kidney transplant 4 weeks to 10 years prior to screening;
4. Patients receiving a stable dose (i.e., no dose adjustments) of TAC-IR for a minimum of 4-7 days at screening;
5. Patients with a screening tacrolimus trough level of 3-9 ng/mL, measured between Day -7 to 0;
6. Women of childbearing potential must have a negative urine pregnancy test at screening;
7. Patients must be willing to commit to and comply with the schedule of study visits.
8. The patient is not scheduled to begin any new medication that could interfere with tacrolimus blood levels, including prescription and over-the-counter medications, herbal, or food supplements (including grapefruit and pomegranate products), or medications listed in [Appendix 1](#).

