**Analysis Methods:**

In general, continuous variables will be summarized with number of non-missing observations, mean, standard deviation (SD), median, minimum, and maximum displayed. Categorical variables will be summarized as counts and percentages.

The primary efficacy endpoint is the Global Composite Score on the RBANS. Raw scores on the RBANS will be age adjusted and converted into a series of Index Scores (reflecting domains such as immediate memory, delayed memory, attention, etc.) which will in turn be combined to generate the aforementioned Global Composite Score, a summary score reflective of overall neuropsychological status (scores have a mean of 100, SD of 15, impairment is typically defined as a score of <78 (1.5 SD below the mean). Descriptive summaries of patients' scores and percentiles at baseline (i.e., Visit 2) and post-baseline (i.e., Visit 3) will be provided. The mean change (absolute change) in -score the RBANS composite score from baseline to post-baseline will be evaluated using paired t-test at 0.05 significance level. A 95% confidence interval (CI) will be constructed for the mean change. Same methods will be used to analyze other cognitive test scores.

CGI-I and PGI-I will be summarized by number and percentages of patients in each category as well as combined categories of improvement (e.g., "Minimum improved", "Much improved", "Very much improved [CGI-I]/Very much better [PGI-I]").

Safety analyses (i.e., ENVARSUS XR exposure, adverse events, and trough level of ENVARSUS XR), as well as vital signs will be summarized descriptively.

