Patients with chronic kidney disease most commonly show cognitive impairments involving attention, memory, executive functions, and mental processing speed. Although data have demonstrated improvements in cognition following kidney transplant and the reversibility of the memory problems evidenced in dialysis, neurotoxicity in transplant patients occurs in >40-50% of the patients treated with tacrolimus. Attention and working memory impairment have been observed in patients treated with sirolimus or tacrolimus, while cyclosporine-treated patients demonstrated performance similar to that of healthy volunteer controls, which may indicate that the cognitive deficit found was partly related to treatment.

Tacrolimus-induced neurotoxicity can occur despite low trough levels; maximum concentration level and fluctuations in serum levels seem more relevant indicators of potential manifested side effects of neurotoxicity. Insomnia and cognitive dysfunction including memory impairment, visual and attention disturbances are two most frequently documented tacrolimus-induced neurotoxic side effects, which may in turn impact patient quality of life and/or work-related productivity.

Neurotoxicity is associated with peak tacrolimus concentrations in transplant as well as autoimmune diseases and shows that the neurotoxicity essentially abates when tacrolimus treatment is discontinued, providing proof that tacrolimus is a reversible neurotoxic agent. The current management of neurotoxicity varies by Investigator and institution, but typically begins with a dose reduction of the tacrolimus, balancing increased risk of acute rejection and graft loss with the desire to improve the side effects observed for a given patient. The results demonstrated in STRATO that showed lower peak concentration and a flatter profile of ENVARSUS XR may result in a reduction of neurotoxicity in kidney transplant patients; therefore, further study of ENVARSUS XR on potential cognitive impact is warranted.

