#### **10.2.2.5 Repeatable Battery for the Assessment of Neuropsychological Status Update (RBANS Update)**

The Repeatable Battery for the Assessment of Neuropsychological Status (RBANS) was developed for the dual purposes of identifying and characterizing abnormal cognitive decline in the older adult and as a neuropsychological screening battery for younger patients. It is widely used in both clinical contexts and clinical trials. While easily tolerated by patients and easily administered, it is also psychometrically robust and sensitive in the detection of even mild expressions of cognitive impairment. The entire battery takes less than 30 minutes to administer, and yields scaled scores for five cognitive domains, known as Index Scores). These domains include Immediate Memory (List Learning and Story Memory), Visuospatial/Constructional (Figure Copy and Line Orientation), Language (Picture Naming and Semantic Fluency), Attention (Digit Span and Coding), and Delayed Memory (List Recall, List Recognition, Story Memory, and Figure Recall). The RBANS utilizes parallel forms, ideal for measuring change over time, and takes approximately 30 minutes to administer.

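### The single-arm RBANS change is tested against zero, so it cannot separate a drug effect from repeat-testing gains or post-transplant recovery

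*Combined protocol and SAP*

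**What the plan says.** Section 7 is the whole design rationale. It credits the open-label switch with "having patients serve as their own control, thus minimizing other confounding factors that may impact cognitive function".

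Section 6.2.1 fixes what is analysed: "The primary efficacy endpoint is the change in cognitive function from Visit 2 to 3 as measured by the Global Cognition Score on the RBANS". The Synopsis (Analysis Methods) says that the mean change "from baseline to post-baseline will be evaluated using paired t-test at 0.05 significance level", so the null is zero change from any cause.

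The question put to the data is causal or nearly so. The Synopsis (Methodology) asks whether the drug "is associated with improved cognitive function relative to that observed with tacrolimus treatment". Section 4.6 goes further and speaks of the switch improving cognition. The formal objectives in section 5 are milder: to assess cognition at baseline and after conversion, in a study labelled exploratory.

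Three other statements bear on the point:

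- Section 4.6 notes that "data have demonstrated improvements in cognition following kidney transplant".
- The inclusion criteria admit "Recipients of a primary or secondary kidney transplant 4 weeks to 10 years prior to screening". Stability refers to the TAC-IR dose, unchanged for at least 4-7 days.
- Section 10.2.2.5 says: "The RBANS utilizes parallel forms, ideal for measuring change over time". No section assigns a form to a visit, and section 10.2.2.6 does not mention alternate forms for the Trail Making Tests.

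The protocol has no continuation arm, run-in or second baseline, and no analysis uses time since transplant.

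**The concern.** Comparing patients with themselves removes differences between patients. It does not remove anything that shifts within a patient between the two visits. Two such shifts are visible in the protocol: the same battery is given again about four months later, and some patients may enter only weeks after transplant, when cognition may still be recovering. Converting raw RBANS scores to age-adjusted scores removes neither.

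Either shift would push the mean change upward, in the hypothesised direction, and the test would count it as improvement. A significant result would then be read as evidence for the drug although the drug had done nothing. Section 7 invites that reading.

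**Working it through.** **Inputs from the documents.** Effect size 0.5, power 80%, one-sided alpha 0.025, 34 evaluable patients, maximum 52 (section 14.1). RBANS population SD 15 (section 14.5.1).

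**Assumed, because the documents are silent.** Retest correlation r of 0.8, range 0.7 to 0.9. Mean non-drug gain of 1, 2 or 3 RBANS points.

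**Step 1: the plan's own figure.** For a paired t-test with standardized change d, power is P(T > t(0.975, n-1)), where T is non-central t with non-centrality d × √n. At d = 0.5, n = 33 gives 0.795 and n = 34 gives 0.808. The 34 reproduces exactly, so the sample-size arithmetic is sound. It is power to detect a mean change of that size, whatever its cause.

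**Step 2: SD of change.** 15 × √(2(1 - r)) gives 11.6 points at r = 0.7, 9.5 at 0.8 and 6.7 at 0.9. At r = 0.8 the planned effect of 0.5 SD of change is 4.7 points.

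**Step 3: chance of a significant improvement when the drug does nothing.** Use the formula of Step 1 with d = gain / SD of change. For 3 points at r = 0.8, d = 3/9.49 = 0.316. The non-centrality is 0.316 × √34 = 1.84, which gives 43%.

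| Non-drug gain | r | n = 34 | n = 52 |
|---|---|---|---|
| 0 | any | 2.5% | 2.5% |
| 1 point | 0.8 | 9% | 11% |
| 2 points | 0.8 | 22% | 32% |
| 3 points | 0.8 | 43% | 61% |
| 3 points | 0.7 | 31% | 45% |
| 3 points | 0.9 | 72% | 89% |

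**Step 4: smallest significant mean gain.** t(0.975, n-1) × SD of change / √n. At r = 0.8 this is 2.03 × 9.49/√34 = 3.3 points, or 2.01 × 9.49/√52 = 2.6 points.

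**Step 5: can Visit 4 measure the drift?** RBANS is collected at Visit 4. The contrast (V3 - V2) - (V4 - V3) equals 2·V3 - V2 - V4. With equal correlations its variance is 6 × 15² × (1 - r), against 2 × 15² × (1 - r) for the simple change, so its SD is √3 = 1.73 times larger. A 0.5 SD effect that is complete by Visit 3 becomes 0.5/1.73 = 0.29, and power is 37% at n = 34 and 53% at n = 52.

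**Step 6: would a retest allowance work as a decision rule?** The documents supply no value. As an illustration, suppose a 3-point allowance, r = 0.8 and no actual drift. The planned 4.74-point effect leaves 1.74 points, so d = 1.74/9.49 = 0.18, and power falls from 81% to 18% at n = 34 (26% at n = 52).

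**The case against.** The strongest reply is that the study is openly single-arm and exploratory. Its formal objectives speak only of outcomes at baseline and after conversion, and the t-test keeps its error rate for the null that it states. RBANS was described as suited to repeated use because it has parallel forms, and section 14 promises a full SAP before database lock. All of this stands, and it lowers the severity. It does not answer the point: the exploratory label does not separate drug from drift, section 4.6 still states a causal aim, and section 7 still claims a protection that the design lacks.

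Four stronger readings are tempting, but the documents do not support them.

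- A reader might infer that scores will rise without the drug. The documents give no drift size. Parallel forms, if rotated, reduce item-specific practice. Section 4.6 does not say that recovery continues beyond 4 weeks, and the share of recent recipients among patients up to 10 years post-transplant is unknown. At r = 0.8 a half-point drift gives only 5-6%.
- A reader might infer that the bias grows with sample size. A fixed drift biases the mean by the same amount at any n. Only the chance of rejecting zero rises.
- A reader might take Visit 4 as a clean drift estimate under unchanged treatment. Section 9.3 allows ENVARSUS XR dose adjustments after Visit 3, and sections 9.4.1 and 9.4.3 require stable co-medication only up to Visit 3. The intervals are four months only nominally. With a start up to 30 days after Visit 2, windows of ±30 days and the start date as anchor (Synopsis, Study Visits), Visit 2 to 3 can span about 3 to 6 months and Visit 3 to 4 about 2 to 6. Table 10-1 anchors on Visit 2 instead. Drift may be front-loaded, and a drug effect may still be accruing.
- A reader might ask for a retest allowance as the bar for success. With no documented value, it could remove most of the power (Step 6).

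**Conclusion.** The point holds. The Visit 2 to Visit 3 test shows whether RBANS changed after conversion, not whether ENVARSUS XR changed it. Section 7's claim is correct for stable patient characteristics only, and the causal aim in section 4.6 goes beyond what this test can support.

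The size is conditional on the assumed drift and retest correlation. At r = 0.8 and a drift of 1 to 3 points, a false attribution occurs in 9-43% of trials at n = 34 and 11-61% at n = 52, against 2.5% nominal. If there is no drift, there is no inflation.

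This is a should-fix. No change to the analysis text can turn the design into a controlled one, but the stated conclusion can be brought into line with it.

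**What to change.** 1. Reword section 7 to say that self-comparison removes stable between-patient differences but not practice, recovery or other changes over time. Limit the efficacy conclusion to change after conversion, without attributing improvement to ENVARSUS XR, and align section 4.6 and the Synopsis.
2. Assign the RBANS parallel forms to Visits 2, 3 and 4 in counterbalanced order from a list made in advance, and record the form used.
3. Pre-specify in the SAP a sensitivity analysis of the primary endpoint with time since transplant as covariate, and a repeat in patients at least 12 months post-transplant. The 12-month cut is a proposal and not a figure from the documents. The transplant date is already needed for eligibility.
4. Report Visit 4 RBANS descriptively, and say in the text why it is not a clean estimate of drift. Do not make an unsourced retest allowance a decision rule.

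The cost is a form list, some SAP text and a small amount of extra analysis, with no new patients or visits. The main downside is a weaker permitted claim. The 12-month subset will also be smaller and less precise.
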